### 3.4 Outcomes

#### Primary outcome

Name	Method and metric	Time points of data collection
Pressure ulcer category II, III, IV, Unstageable, DTI at heels or sacrum	
 
• Clinical assessment using the NPUAP/EPUAP 2014 PU classification system
 
• Proportions developed from baseline until end of study (cumulative incidence)
 
	D0 and once daily

## Secondary outcomes

Name	Method and metric	Time points of data collection
Pressure ulcer category II, III, IV, Unstageable, DTI at heels or sacrum	
 
• Clinical assessment using the NPUAP PU classification system
 
• Proportions developed per 1000 bed days (incidence)
 
	D0 and once daily
Pressure ulcer category I (non-blanchable erythema) at heels and/or sacral area	
 
• Clinical assessment using the NPUAP PU classification system
 
• Proportions developed from baseline until end of study (cumulative incidence)
 
	D0 and once daily
Pressure ulcer category I (non-blanchable erythema) at heels and/or sacral area	
 
• Clinical assessment using the NPUAP PU classification system
 
• Proportions developed per 1000 bed days (incidence)
 
	D0 and once daily
Days free of sacral and/or heels pressure ulcers category I, II, III, IV, DTI	
 
• Clinical assessment using the NPUAP PU classification system
 
• Number
 
	D0 and once daily
Resources associated with heel and sacral PU prevention	
 
• Preventive dressings (n), time for dressing application (minutes; data source: estimation)
 
• Type of support surface (standard, special elastic foam, viscoelastic foam, low air loss overlay/mattress, alternating air mattress; data source: clinical records and direct observation)
 
• Type of turning (30° degrees left/right, supine, prone, other; data source: clinical records)
 
	D0 and once daily
Resources associated with heel and sacral PU treatment	
 
• Wound assessments (number and times; data source: clinical records and estimation)
 
• Wound infection diagnoses, e.g. swabs, biopsies (number, times; data source: clinical records and estimation)
 
• Therapeutic primary and secondary dressings (numbers, types), time for dressing application/changes (minutes; data source: clinical records and estimation)
 
• Debridement (numbers and types incl. material; data source: clinical records and estimation)
 
• Systemic antimicrobial treatment because of PU wound (number, types; data source: clinical records)
 
	D0 and once daily

Heel and sacral PU healing	
 
• Complete epithelialization
 
• Mean (days)
 
	D0 and once daily
----------------------------	---	-------------------

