### Secondary objectives

- To determine if preventive silicone dressings (Mepilex® border) applied to the heels and to the sacrum in addition to PU standard prevention reduce the PU incidence density category II, III, IV, and deep tissue injury (DTI) compared to PU standard prevention alone in at high or very high risk hospital patients.
- To determine if preventive silicone dressings (Mepilex® border) applied to the heels and to the sacrum in addition to PU standard prevention reduce the cumulative PU incidence category I compared to PU standard prevention alone in at high or very high risk hospital patients.
- To determine if preventive silicone dressings (Mepilex® border) applied to the heels and to the sacrum in addition to PU standard prevention reduce the PU incidence density category I compared to PU standard prevention alone in at high or very high risk hospital patients.
- To determine if preventive silicone dressings (Mepilex® border) applied to the heels and to the sacrum in addition to PU standard prevention increase days free of PUs category I, and category II, III, IV, and DTI compared to PU standard alone in at risk hospital patients.
- To determine if preventive silicone dressings (Mepilex® border) applied to the heels and to the sacrum in addition to PU standard prevention are cost effective.

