Skin and tissue inspections are conducted and study variables are collected daily by instructed researchers/research assistants/study nurses in agreement with the ICU and general ward staff. The following educational activities will be conducted before and during the trial:

- Initiation visit/kick-off meeting explaining the study design, procedures, data collection and documentation methods
- One hour skin and PU classification instruction, followed by an online examination PUCLAS3 (Beeckman, Schoonhoven 2014) for all study nurses/research assistants doing skin examinations
- Unannounced patient visits by the principle investigator for duplicate data collection and skin examination

Research assistants/study nurses/researchers follow up all included patients once daily for ensuring study compliance, monitoring correct dressing use and fit, doing skin inspections at the heels and sacral area and for monitoring the health condition including daily

documentation of PU risk and resource use regarding dressings and possible PU treatment (dressings, wound care procedures).

The study/follow-up ends if:

- The patient is no longer at “high” or “very high” PU risk according to the Charité standard (Figure 1) and if no sacral or heel PU developed or
- Complete healing of a within the study period developed heel or sacral PU or
- An adverse event (AE) related to the preventive dressings occurred or
- The patient wishes to withdraw or
- A severe form of protocol violation occurred (e.g. non-wearing of the dressings for more than 24 hours) or
- The patient dies or
- The patient is transferred to another care setting outside the Charité Campus Virchow or is discharged from the hospital

Adherence to the study protocol is improved using the following strategies:

- Kick-off meetings and training on the participating ICUs and EDs
- Subject cards at the bedside (Appendix 3)
- Once daily follow-up visits and assessments by researchers including checks of dressing fit
- Monthly status reports about recruitment on the participating wards
- Unannounced patient visits by the PI for duplicate data collection and skin examination

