### 3.6 Sample size

We are planning a study of independent cases and controls with 1 control per case. Prior data of the internal quality management indicate that the average PU incidence at the ICUs of the Charité is 0.06 per month. We expect that the cumulative PU incidence for experimental subjects will be 0.01 (RR 0.17). In order to test this hypothesis we will need to study 211 experimental patients and 211 control patients to be able to reject the null hypothesis that the PU incidence in the intervention and control groups is equal with a probability (power) of 0.8. The Type I error probability associated with this test of this null hypothesis is 0.05 (two-sided). We will use the chi-squared test statistic to evaluate this null hypothesis. To prevent a possible loss of follow-up of 10%, 464 patients in total are to be included. This total sample size is comparable to a previous trial using a similar intervention and design (Santamaria et al. 2013a). The “true” PU heel and sacral PU incidence in the study might be higher, because we will include only “high” and “very high risk” patients.

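### The incidence-density outcomes use an undefined bed-day denominator that, read literally, counts days after the first ulcer and would modestly dilute a true effect

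*Combined protocol and SAP*

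**What the plan says.** Two secondary objectives in section 2.2 concern incidence density, one for category I and one for the more severe ulcers. The latter asks whether dressings "reduce the PU incidence density category II, III, IV, and deep tissue injury (DTI) compared to PU standard prevention alone". In the secondary outcomes table of section 3.4, both are measured as "Proportions developed per 1000 bed days (incidence").

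Section 3.3 lists when follow-up ends. Leaving the high-risk categories ends it only on a condition: "and if no sacral or heel PU developed or" another listed stop applies. For a patient with an ulcer the corresponding stop is "Complete healing of a within the study period developed heel or sacral PU". Other stops apply to everyone, including when the patient "is transferred to another care setting outside the Charité Campus Virchow or is discharged from the hospital", and also death, withdrawal, a dressing-related adverse event or a severe protocol violation.

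Nothing in the plan limits bed days to days at risk, stops the count at the first ulcer, or says whether repeat ulcers count. For secondary outcomes, section 5.2 refers to methods similar to those for the primary outcome and names chi-squared, t- and Mann-Whitney tests. It names no method for person-time rates.

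**The concern.** An incidence density estimates how fast first events occur among people who can still have one. A patient who already has the qualifying ulcer has left that group. Here the ulcer also keeps the patient under observation: loss of high-risk status releases an ulcer-free patient but not a patient with an ulcer. On the literal reading, the outcome lengthens its own denominator.

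If the dressings prevent ulcers, the control arm has more ulcers and so more post-ulcer days. Its rate is diluted more than that of the dressing arm, and the contrast shrinks. The reported density would then partly reflect healing time and length of stay rather than prevention. Two secondary objectives depend on this metric.

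**Working it through.** **Inputs from the plan.** Section 3.6 uses 0.06 for controls ("the average PU incidence at the ICUs of the Charité is 0.06 per month", which the plan treats as the control proportion) and 0.01 with dressings, with 211 per arm, 80% power and two-sided alpha 0.05.

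**The plan's own figure.** The pooled two-proportion formula without continuity correction is
n = [1.96·√(2·0.035·0.965) + 0.8416·√(0.06·0.94 + 0.01·0.99)]² / 0.05² = (0.509 + 0.217)² / 0.0025 ≈ 211 per arm.
Adding 10% gives 422 × 1.1 = 464. Both agree with section 3.6, so 6% vs 1% is the right pair of rates to work from. The plan states no expected density, follow-up length or healing time.

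**Assumed inputs.** s = mean at-risk days per patient, 8 to 12. h = mean days followed after onset, 10 to 30, equal in both arms.

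**Share of post-ulcer days in controls.** 0.06 / (0.06 + 0.01) = 86%.

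**Formulas, per 1000 days.** At-risk denominator: 1000p / s. All bed days: 1000p / (s + p·h).

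| s | h | Control rate | Dressing rate | Rate ratio | Difference | Shrinkage of difference |
|---|---|---|---|---|---|---|
| 8 | 0 | 60/8 = 7.50 | 10/8 = 1.25 | 0.167 | 6.25 | – |
| 8 | 10 | 60/8.6 = 6.98 | 10/8.1 = 1.23 | 0.177 | 5.74 | 8% |
| 8 | 30 | 60/9.8 = 6.12 | 10/8.3 = 1.20 | 0.197 | 4.92 | 21% |
| 12 | 0 | 60/12 = 5.00 | 10/12 = 0.83 | 0.167 | 4.17 | – |
| 12 | 10 | 60/12.6 = 4.76 | 10/12.1 = 0.83 | 0.174 | 3.94 | 6% |
| 12 | 30 | 60/13.8 = 4.35 | 10/12.3 = 0.81 | 0.187 | 3.54 | 15% |

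**Check with a second model.** The table gives both arms the same at-risk time. In practice a patient with an ulcer has a shorter time at risk. Let L be the days followed without an ulcer and t = L/2 the days to the first ulcer. The denominator is (1−p)L + p·t, plus p·h if all bed days count. With L = 10 and h = 10:
- At risk: 60/9.70 = 6.19 vs 10/9.95 = 1.01; ratio 0.162, difference 5.18.
- All bed days: 60/10.30 = 5.83 vs 10/10.05 = 1.00; ratio 0.171, difference 4.83.

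Over L = 5 to 20 and h = 5 to 30, the ratio moves from 0.162 to between 0.165 and 0.210, and the difference shrinks by 2% to 31%. The direction is the same throughout.

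**When the direction fails.** In the first model, the ratio is unchanged when p·h is equal in the two arms. At 6% vs 1%, dressing-arm ulcers would need about six times as many post-ulcer days each. If p and h are both equal across arms, the two denominators grow alike and the ratio stays at 1.

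**The case against.** The strongest reply is that the plan gives no rule for the denominator. A reader might infer that it instructs the analyst to count healing days. It does not: bed days are undefined, and counting them is the literal reading only. This limits how firmly the point can be put, but it does not remove it, because nothing in the plan points to any other count.

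Second, section 5.2 already has Kaplan-Meier, log-rank and Cox analyses of time to a new ulcer, to which healing days do not contribute. This is true and limits the harm. Those analyses neither define nor correct the density, which is a separate outcome with its own objectives.

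Third, the shift is small against sampling error. With 211 per arm, about 12.7 and 2.1 events are expected (211 × 0.06 and 211 × 0.01). The standard error of the log rate ratio is about √(1/12.7 + 1/2.1) = 0.74, which gives a 95% interval of roughly 0.04 to 0.72 around 0.167. The table's shifts are 0.04 to 0.17 on the log scale, or about 0.05 to 0.22 standard errors. This stands. The upper end also needs long post-onset follow-up against a short at-risk stay, and discharge, transfer and death cap those days.

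Fourth, the bias is conservative: with similar post-ulcer stay it does not favour a false claim of superiority. This also stands.

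**Conclusion.** The point holds as a defect in how two secondary outcomes are defined. On the literal reading, and if the dressings work as planned with similar post-ulcer stay in both arms, the density contrast is attenuated. For category II+ the rate ratio moves from 0.167 to between 0.174 and 0.197, and the rate difference shrinks by 6% to 21%, given 8 to 12 at-risk days and 10 to 30 post-onset days. Those durations are assumptions, and the effect is modest.

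Three stronger readings are tempting, but the documents do not support them:

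- **The density is biased whatever the truth.** With no true effect and equal post-ulcer stay, there is no such bias.
- **The category I density is hit hardest.** The plan gives no category I rate. Section 3.4 measures healing by complete epithelialization, while Appendix 4 describes category I as intact skin, so it is unclear when such a lesion counts as healed. No category I figure can be derived.
- **The main result is at risk.** The primary outcome is a proportion of patients, so the primary outcome, the sample size and the time-to-event analyses are unaffected.

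**What to change.** In section 3.4, define each density as patients with a first qualifying ulcer per 1000 patient-days, counted from D0 to that outcome's first qualifying ulcer or the end of follow-up, whichever comes first. The person-time must be specific to the outcome:

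- **Category II+ (including unstageable and DTI):** days with only a category I ulcer stay in the denominator, since the patient can still have the event.
- **Category I:** person-time ends at the first ulcer of any category.
- **Heel and sacral repeats (section 5.2):** count to the first event at that site.

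In section 5.2, compare arms with a person-time method, for example Poisson regression with a log person-time offset, rather than a chi-squared or t-test. Keep the all-bed-days rate as a descriptive figure for comparability. Days after the first event still serve the healing and resource-use outcomes.

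Skin status is already recorded daily, so no new data are needed. The cost is one added definition and a little analysis work.

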**Figure 3. Data collection and management**

## 5.2 Statistical methods

Depending on the level of measurement (nominal, ordinal, continuous) variables will be described using absolute and relative frequencies or arithmetic means, medians and spread parameters (minimum, maximum, interquartile ranges, standard deviations). Baseline demographic (age, gender, PU risk etc.) and clinical characteristics (e.g. medical diagnoses, duration of ventilation) of each group will be displayed in a table.

The primary end point PU incidence category II, III, IV, DTI at heels and/or sacrum will be compared using a Chi-squared test. This will be the main analysis of this primary outcome. A logistic regression will be applied to adjust for baseline covariates. An alpha level of 5% (two-sided) will be applied. Kaplan-Meier analyses and logrank test will be used to compare the times to development of a new PU between groups. Multiple Cox regression analysis will be performed to adjust for potential confounders. Data will be analysed as intention to treat.

Secondary outcomes will be analysed in a similar way. Depending on the level of measurement (nominal, ordinal, continuous) secondary outcomes will be described using absolute and relative frequencies or arithmetic means, medians and spread parameters (minimum, maximum, interquartile ranges, SDs). Chi-squared or t-tests will be applied to compare groups. In case of normality assumption being violated, the Mann-Whitney U test will be used instead of t-test.

For daily measurements, missing values will be imputed via LOCF method, and the results will be compared to those without imputation.

A cost effectiveness analysis (CEA) comparing both groups will be conducted. Quantities of used preventive dressings including labor costs for application in the intervention group and quantities of used PU treatment materials (e.g. dressings, time) will be documented. Current market prizes in Euro will be used to calculate the total costs per group. An incremental cost effectiveness ratio (ICER) will be calculated by dividing the mean differences in costs by the mean differences in effects. In order to make results comparable a similar approach like the work by Santamaria et al. 2013b will be used.

All analytic steps including the CEA will be repeated for the two subgroups heel PUs and sacral PUs.

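### PU-free days is a raw count over follow-up of no fixed length, and the tests named for numeric secondary outcomes have little power on it; assign the objective to the planned time-to-event methods

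*Combined protocol and SAP*

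**What the plan says.** The secondary objectives (section 2.2) ask whether the dressings "increase days free of PUs category I, and category II, III, IV, and DTI compared to PU standard alone in at risk hospital patients". The matching row of the secondary outcomes table (section 3.4) reads "Days free of sacral and/or heels pressure ulcers category I, II, III, IV, DTI". Its metric is a number, collected at D0 and once daily, with no window or denominator. The incidence rows in the same table are expressed per 1000 bed days.

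Follow-up has no fixed last day; Table 1 runs to D1 + x. Section 3.3 ends it at loss of high-risk status without a PU, healing of a PU, withdrawal or death, and also in these cases:
- "The patient is transferred to another care setting outside the Charité Campus Virchow or is discharged from the hospital"
- "An adverse event (AE) related to the preventive dressings occurred"
- "A severe form of protocol violation occurred (e.g. non-wearing of the dressings for more than 24 hours"

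Section 5.2 states, in the paragraph on the primary endpoint, that "Kaplan-Meier analyses and logrank test will be used to compare the times to development of a new PU between groups", with Cox regression for adjustment. The next paragraph opens by saying that secondary outcomes will be handled similarly. It then says "Chi-squared or t-tests will be applied to compare groups", and "In case of normality assumption being violated, the Mann-Whitney U test will be used instead of t-test".

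**The concern.** A patient without a PU scores the days observed. Quick recovery, early transfer and early death therefore all give a low score, and a long stay at high risk gives a high one. Most patients are expected to have no PU, so most of the variation in the count is variation in length of stay. A t-test or Mann-Whitney test treats a short stay as a poor result instead of as incomplete information. Last observation carried forward does not help, because there is no horizon to carry a value to.

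At stake is a stated secondary objective. Tested as named, it would probably show no difference even if the dressings worked as planned, although the daily inspections support a well-powered comparison.

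A second, smaller issue concerns balance between arms. A dressing-related adverse event, and the only example given of a severe violation, can end follow-up only in the dressing arm. Each such exit lowers that arm's count without any ulcer.

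**Working it through.** **Inputs from the protocol.** Section 3.6 gives 0.06 against 0.01, two-sided alpha 0.05, power 0.8 and 211 per arm. These rates are for the primary endpoint and exclude category I.

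**Assumptions not in the documents.** Stays are exponential with mean L of 5, 10 or 20 days. The PU hazard is constant and set so that a proportion p develops a PU before the stay ends. Any-PU rates including category I are taken as 20% against 10%, or 30% against 15%.

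**The plan's own figure.** With pooled variance and no continuity correction, n = [1.960·√(2·0.035·0.965) + 0.842·√(0.06·0.94 + 0.01·0.99)]² / 0.05² = 210.9, so 211 per arm. This reproduces. The plan gives no figure for PU-free days.

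**Analytic check of the t-test.** Let x = min(time to PU, stay). For exponential stays, mean(x) = SD(x) = (1−p)L. At 6% against 1%:
- Difference in means: (0.99 − 0.94)L = 0.05L, or 0.5 day at L = 10.
- z = 0.05 / √((0.94² + 0.99²)/211) = 0.53, whatever L is.
- Power: Φ(0.53 − 1.96) + Φ(−0.53 − 1.96) = 8.3%.
- Probability that the mean difference has the wrong sign: Φ(−0.53) = 29.7%.
- Probability that it is significant in the wrong direction: Φ(−0.53 − 1.96) = 0.6%.
- n per arm for 80% power: (1.960 + 0.842)²·(0.94² + 0.99²)/0.05² ≈ 5,850.

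**Simulation, 211 per arm, no early exits.** The last two columns are analytic.

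| PU rates | t-test | Mann-Whitney | log-rank | wrong sign | n per arm, t-test 80% |
|---|---|---|---|---|---|
| 6% vs 1% | 8–9% | 7–8% | 85–87% | 30% | about 5,850 |
| 20% vs 10% | 22–24% | 18–20% | 87–89% | 11% | about 1,140 |
| 30% vs 15% | 50–52% | 39–41% | 99% | 2% | about 420 |

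**Other stay distributions, 6% vs 1%.** With a 3-day minimum plus an exponential remainder, the t-test and Mann-Whitney test have 8–12% power and log-rank 85–86%. With lognormal stays (mean/SD 7/5, 10/8 and 14/12 days, minimum 3 days) the figures are 8–9%, 8–10% and 84–86%. In the lognormal runs length of follow-up explains 92–93% of the variance of the count.

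**Early exits in the dressing arm only.** Assume a random share of dressing-arm stays is multiplied by a Uniform(0,1) factor. A shortened stay then has a mean count of about 0.497L instead of 0.99L. The gain of 0.05L is cancelled when 0.05/(0.99 − 0.497) = 10.1% of stays are shortened. If there is no true effect (6% in both arms), rejection rates are:

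| Stays cut short | t-test | Mann-Whitney | log-rank |
|---|---|---|---|
| 2% | 5% | 5% | 5% |
| 5% | 6% | 6% | 5% |
| 10% | 9% | 10% | 5% |
| 20% | 17% | 26% | 5% |

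The log-rank result assumes that exits are unrelated to PU risk.

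**The case against.** The strongest reply is that the plan already contains the remedy. The time-to-PU sentence in section 5.2 is not restricted by category, and secondary outcomes are to be handled similarly. The t-test sentence is generic wording by level of measurement. Incidence per 1000 bed days is planned for category II and above and for category I, so exposure time is accounted for elsewhere. This stands in part: a benefit could still show in those analyses. But the text does not assign the time-to-event methods to this count, and the only tests it then names for numeric data are the ones that perform badly.

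A reader might infer that the count would often point the wrong way, or report benefit as harm. The documents do not support that. The 30% wrong-sign figure belongs to rates that leave out category I and describes mostly non-significant differences; it falls to 11% and 2% at the higher assumed rates. A significant result in the wrong direction occurs in under 1% of trials without early exits.

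A reader might also infer that exits confined to the dressing arm bias the comparison. The documents give no exit rate and suggest that it may be low. Section 7.1 says that adverse events from preventive use had not been reported, and section 3.3 has dislodged dressings changed at once. At 2–5% of stays the named tests are close to valid, only weak.

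It is also fair to say that time to first PU is not the same quantity as PU-free days. Healing is recorded as complete epithelialization, while category I is intact skin, so it is unclear whether a resolved category I ends follow-up. If it does not, later PU-free days are ignored.

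**Conclusion.** The concern holds, mainly as a loss of power on one secondary objective. Tested as named, the raw count has about 8% power at the planning rates against about 86% for log-rank. At assumed any-PU rates of 20% against 10% it has about 18–25% against 87–89%, and at 30% against 15% about 39–52% against 99%. Stay lengths and any-PU rates are assumptions, but the gap persists over the range tried. Bias from dressing-arm exits is possible and matters only from about 10% of stays, a rate for which the documents give no support. The primary chi-squared test, the sample size and the incidence-density outcomes are unaffected.

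**What to change.** Amend section 5.2 as follows:
- Do not test the raw day count. Report it by arm with observed days as denominator, and tabulate ends of follow-up by reason and arm.
- State that inference for the PU-free-days objective uses time to first sacral or heel PU, censored at end of follow-up, by Kaplan-Meier, log-rank and Cox.
- Define the event, including Unstageable, which the primary outcome lists and this row omits. Report any category (I and above) and category II and above, because the objective can be read as two measures.
- Use log-rank for the test. At 1% the dressing arm has no event in about 0.99²¹¹ = 12% of trials, so ordinary Cox may give no finite hazard ratio; plan a penalised or exact estimate. About 211 × (0.06 + 0.01) = 15 events allow few covariates.
- State the limits. Time to first PU differs from the day count and ignores days after a PU has resolved, and censoring at recovery, exit or death may be informative.

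A competing-event sensitivity analysis for death is optional. So is a restricted mean PU-free time, which needs a horizon fixed in advance and has less power than log-rank (to day 14 at 6% vs 1%: 82%, 73% and 50% at mean stays of 5, 10 and 20 days).

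The cost is SAP wording and a little extra analysis. No new data are needed, since skin is inspected daily.

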##### Exclusion criteria

[figure not shown]
- Patients at end of life/dying patients
- Existing PU or other skin/tissue lesion (e.g. scars) at heels or sacral skin
- Positioning on air fluidized beds
- Known allergy to Mepilex® dressings
- Patients who cannot be repositioned due to medical reasons (e.g. cardiovascular instability, suspected or actual spinal cord injury)
- Trauma to sacrum and/or heels
- Exclusion based on complicated or not possible positioning of patients with the following diagnoses (ICD-10-GM version 2015): 66.2; J80.0; S06.-; G93.2; I60.-; I63.-
- Exclusion due to certain procedures (OPS version 2015): 8-390.0; 8-390.3; 8-390.4; 8-852

As this study does not involve any drugs, systemic agents or any other invasive techniques, patients would be eligible even if they participate in another trial.

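### Healing time exists only for patients who develop an ulcer after randomisation, so the planned between-arm test of it is not a randomised comparison

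*Combined protocol and SAP*

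**What the plan says.** The secondary outcomes table in section 3.4 includes heel and sacral ulcer healing, defined as "Complete epithelialization" and summarised as a mean number of days. It names no analysis population and gives no rule for ulcers still open when follow-up ends.

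Section 3.2 excludes patients with "Existing PU or other skin/tissue lesion (e.g. scars) at heels or sacral skin". Any ulcer that heals during the study must therefore have arisen after randomisation.

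For secondary outcomes, section 5.2 states that "Chi-squared or t-tests will be applied to compare groups", with Mann-Whitney U as the fallback. Healing is neither exempted nor labelled descriptive. Survival methods are named for a different event: "Kaplan-Meier analyses and logrank test will be used to compare the times to development of a new PU between groups". The analysis set is given in one sentence: "Data will be analysed as intention to treat". The missing-data rule is "For daily measurements, missing values will be imputed via LOCF method, and the results will be compared to those without imputation".

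Section 3.3 lists the events that end follow-up. One is "Complete healing of a within the study period developed heel or sacral PU or". Others apply whether or not an ulcer has healed: death, withdrawal, a dressing-related adverse event, a severe protocol violation, and "The patient is transferred to another care setting outside the Charité Campus Virchow or is discharged from the hospital".

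**The concern.** Developing a heel or sacral ulcer is the primary outcome, and the plan expects its frequency to differ sixfold between arms. Patients with a healing time are thus selected by the effect under study. If the dressings mainly prevent mild ulcers, those that remain in the dressing arm are on average worse, and healing looks slower there even if the dressings do not affect healing. If they mainly prevent severe ulcers, the distortion runs the other way. The documents do not show which applies, so neither the direction nor the size of the bias can be given. A p-value from this comparison could be read as a treatment effect on healing, and it is not one.

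There is a second, separate problem. An ulcer still open at death, discharge or transfer has no healing day, and the plan does not say how it enters the mean. Carrying the last observation forward only repeats the unhealed state and produces no healing day.

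**Working it through.** **Inputs.** From section 3.6: ulcer incidence 0.06 (control) and 0.01 (dressings), 211 per arm, two-sided alpha 0.05, power 0.80, 464 in total after 10% for loss. The share of ulcers seen to heal before follow-up ends, h, is not in the documents. I take 100% as the case most favourable to the plan and vary it from 25% to 100%.

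**The plan's own sample size.** Pooled-variance formula without continuity correction:

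n = [1.96·√(2 × 0.035 × 0.965) + 0.8416·√(0.06 × 0.94 + 0.01 × 0.99)]² / 0.05² = (0.5094 + 0.2167)² / 0.0025 = 210.9, so 211 per arm.

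Then 422 × 1.10 = 464.2, so 464, or 232 per arm. Both figures are reproduced.

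**Expected patients with an ulcer at 211 per arm.** Control: 211 × 0.06 = 12.66. Dressings: 211 × 0.01 = 2.11. Together that is 14.77 of 422, or 3.5% of patients. At 232 per arm: 13.9 and 2.3.

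**Chance of very few dressing-arm cases (binomial).**
- 211 per arm: P(0) = 0.99^211 = 0.120. P(1) = 211 × 0.01 × 0.99^210 = 0.256. P(at most 1) = 0.376.
- 232 per arm: P(0) = 0.99^232 = 0.097. P(1) = 232 × 0.01 × 0.99^231 = 0.228. P(at most 1) = 0.325.

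**If only a share h is seen to heal** (planning rates, 211 per arm; replace 0.01 by 0.01 × h):

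| h | P(no healed case, dressing arm) | P(at most one) |
|---|---|---|
| 100% | 12% | 38% |
| 75% | 20% | 53% |
| 50% | 35% | 72% |
| 25% | 59% | 90% |

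**If the rates differ from planning** (211 per arm):

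| Control vs dressings | Expected cases | P(at most one), h = 100% | P(at most one), h = 50% |
|---|---|---|---|
| 6% vs 1% | 12.7 vs 2.1 | 38% | 72% |
| 12% vs 2% (same relative risk) | 25.3 vs 4.2 | 7% | 38% |
| 6% vs 3% (relative risk 0.5) | 12.7 vs 6.3 | 1% | 17% |

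**What a test could show.** With 13 versus 2 healing times, a two-sample t-test (13 df, noncentrality d·√(13 × 2/15)) reaches 80% power only at d of about 2.3 SD. With 13 versus 1, the smallest two-sided Mann-Whitney p-value is 2/14 = 0.14, so significance at 5% is impossible.

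The selection argument uses none of these numbers. It follows from sections 3.2, 3.4 and 5.2 read together.

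**The case against.** Several points on the other side have force.

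- **Ulcer patients are kept in follow-up.** Under section 3.3, a fall in risk category ends follow-up only for patients without an ulcer, and complete healing is itself an end point. This reduces truncation. It does not remove it, because death, discharge and transfer still apply.
- **The test wording is generic.** The paragraph on secondary outcomes in section 5.2 opens by referring back to the approach for the primary outcome, which includes Kaplan-Meier, logrank and Cox methods. Healing could therefore be read as a time-to-event analysis. That would deal with unhealed exits, but it would still compare arms only among patients who developed an ulcer.
- **Healing has little weight in the plan.** It is not among the objectives in section 2.2. Ulcer-free days, which are defined for every randomised patient, are both an objective there and an outcome in section 3.4. This stands and limits the severity.
- **The rates are uncertain.** Section 3.6 gives 0.06 as a monthly ICU average and says incidence in the trial might be higher. The small-number figures therefore belong to one scenario and need the range shown.

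Two stronger readings are tempting and are not supported. A reader might infer from the 38% that the comparison often cannot be computed. One dressing-arm case still gives a mean, and a pooled t-test on 13 versus 1 (12 df) and a Mann-Whitney U can both be calculated, however uninformative. On ulcer cases alone, the comparison is undefined only with zero cases: 12% at 211 per arm, 10% at 232. A reader might also infer that long healing times will certainly be dropped from the mean. That presumes complete-case handling, whereas the plan is silent.

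**Conclusion.** The point holds. As written, the plan applies a between-arm test to an outcome defined only after the event the dressings are meant to prevent. The intention-to-treat statement cannot be met for an outcome undefined in about 96% of patients on the planning rates. No other section cures the selection, and it remains at any incidence. That healing time is confined to ulcer cases is inferred from the exclusion criterion and the outcome definition; the plan does not say so itself.

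Truncation is a real but lesser problem, whose extent cannot be sized because the documents give no healing, discharge or death rates. Sparse dressing-arm data are likely on the planning rates and become much less likely with higher incidence or a smaller effect.

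The consequence is limited to one secondary outcome. The primary analysis does not depend on it, so this is a minor improvement.

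**What to change.** In section 5.2, state that healing is reported descriptively among patients who develop a heel or sacral ulcer, with no between-arm test. List each ulcer by arm, with days to healing or days to exit unhealed, and the reason for exit.

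For the randomised comparison, rely on the outcome already planned in sections 2.2 and 3.4: days free of heel or sacral ulcers, in all randomised patients. State the observation window over which those days are counted. Under section 3.3, length of follow-up depends on ulcer status: patients without an ulcer leave when their risk falls, while those with one may stay until it heals. A raw count of free days, or a rate per observed day, would carry that dependence into the result.

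The cost is SAP wording only, since skin status is already recorded daily. The trial gives up a p-value for healing time.
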